Study 1289.18 was conducted to assess safety, tolerability, PK and pharmacodynamics (PD) of BI 409306 25 mg, 50 mg, or 100 mg once a day (q.d.) for 14 days in patients with mild-to-moderate schizophrenia. Satisfactory safety and tolerability were observed while PK mirrored that of healthy volunteers. Recently completed study 1289.6 (proof of concept study in patients with cognitive impairment associated with schizophrenia (CIAS)) failed to achieve the primary endpoint of improving cognition as assessed by the MATRICS Consensus Cognitive Battery (MCCB), however demonstrated acceptable safety and tolerability at all doses. The percentage of subjects with any AE increased with increasing BI 409306 dose, ranging from 33.3% in the 10 mg group to 53.5% in the 100 mg group. The incidence of AEs in the 10 mg and 25 mg dose groups was similar to that of the placebo group. Most AEs were mild or moderate in intensity, with only 2 subjects in the BI 409306 groups and 4 subjects in the placebo group experiencing severe adverse events (AEs). Most striking was the finding that Serious AEs (SAEs), including 8/8 psychiatric SAEs, were only reported in the placebo group vs. none in the active arms. Further, it was noted that results of the C-SSRS showed suicidal ideation was reported in no subjects in the 10 mg group, 1 subject (1.2%) in the 25 mg group, 2 subjects (2.5%) in the 50 mg, 1 subject (1.2%) in the 100 mg group, and 6 subjects (3.6%) in the placebo group. It was further noted that the severity of the suicidal ideation present was more severe within the placebo subjects, with 3 placebo subjects reporting "Active suicidal ideation with any methods (not plan) without intent to act" and one subject reporting "Active suicidal ideation with some intent to act, without specific plan" vs. zero such findings in the active dose groups [[c01694347-09](#); [c09340078-01](#)].

None of the safety data presented a safety issue for further clinical trials.

For a more detailed description of the BI 409306 profile, including pharmacokinetics and pharmacodynamics, please refer to the current Investigator's Brochure (IB) [[c01694347-09](#)].

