#### 2.1.2 Primary endpoint(s)

The primary endpoint is time to first relapse until study end (planned at 28 weeks). Time of relapse will be obtained by selecting the earliest date from any, or all of the following 6 criteria:

- Time to hospitalization (involuntary or voluntary admission), intensive outpatient therapy or use of home treatment, as an alternative to hospitalization, for decompensation of schizophrenia symptoms
- Time to an assessment on the Clinical Global Impressions - Severity (CGI-S) of  $\geq 5$  (markedly ill) and either:
  - an increase on any of the following individual PANSS items: conceptual disorganization, hallucinatory behavior, suspiciousness, unusual thought content - to a score  $> 4$  with an absolute increase of  $\geq 2$  on that specific item since randomisation
  - or
  - an increase on any of the following individual PANSS items: conceptual disorganization, hallucinatory behavior, suspiciousness, unusual thought content - to a score  $> 4$  and an absolute increase of  $\geq 4$  on the combined 4 PANSS items since randomisation
  - or
  - PANSS total score increase of  $\geq 25\%$  relative to baseline score or an increase of  $\geq 10$  points if baseline score was  $\leq 40$
- Time to a prescription for a new antipsychotic or time to an increase in dose of an ongoing antipsychotic medication for significant worsening of schizophrenia symptoms
- Time to clinically significant homicidal ideation, in the investigator's judgement
- Time to suicidal behavior, or time to assessment of suicidal ideation type 4 or 5 on the Columbia Suicide Severity Rating Scale (C-SSRS)

- Time to deliberate self-injury and/or violent behaviour resulting in suicide or in clinically significant injury to the patient or another person or property damage, in the investigator's judgement

[figure not shown]

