#### 5.2.5 Other safety parameters

##### 5.2.5.1 Assessment of Suicidality

Suicidality should be monitored closely during the study period. Suicidal thoughts and behavior will be assessed by the Columbia-Suicide Severity Rating Scale (C-SSRS) ([R08-1147](#)). An electronic version utilizing a tablet solution will be used for this trial.

The C-SSRS is a semi-structured, investigator-rated interview, developed by clinical experts in cooperation with the FDA, assessing both suicidal behavior and suicidal ideation. It does not give a global score, but provides some categorical and some severity information specifically for behavior and ideation.

The C-SSRS interview may be administered by any type of physician, psychologist, clinical social worker, mental health counselor, nurse, or coordinator with C-SSRS training. It has a typical duration of five minutes, and causes only a low burden on subjects. At a minimum, the interview consists of 2 screening questions related to suicidal ideation and 4 related to suicidal behavior, and may be expanded to up to 17 items in case of positive responses. Free text entries are allowed for; the investigator has to directly evaluate the scale and write a report.

The C-SSRS has been widely used in large multinational clinical trials. The C-SSRS will be administered at the Screening Visit/Visit 1 (using the 'baseline/ screening' version) with the aim to exclude patients with active moderate or severe symptomatology

[figure not shown]
within a specified time prior to the screening or screening visit. The lifetime history of suicidal ideation and behavior will also be recorded.

After the screening visit, the assessment 'since last visit' version will be performed at each clinic or phone visit. The investigator is to review positive and negative reports for plausibility and clinical relevance. Doubtful reports may be repeated or reports may be validated by a consulting psychiatrist. If there is a confirmed positive report of suicidal behavior or suicidal ideation type 4 or 5 after start of trial, the investigator is to immediately interview the patient, and/or is to consult a psychiatrist. If the positive report is confirmed, appropriate actions for the patient's safety have to be initiated.

All C-SSRS reports of suicidal ideation type 4 or 5 and all reports of suicidal behavior must be reported as separate SAEs by the investigator.

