### **Serious adverse event**

A serious adverse event (SAE) is defined as any AE which fulfils at least one of the following criteria:

- results in death,
- is life-threatening, which refers to an event in which the patient was at risk of death at the time of the event; it does not refer to an event that hypothetically might have caused death if more severe.
- requires inpatient hospitalisation or
- requires prolongation of existing hospitalisation,
- results in persistent or significant disability or incapacity, or
- is a congenital anomaly / birth defect,
- or
- is deemed serious for any other reason if it is an important medical event when based on appropriate medical judgement which may jeopardise the patient and may require medical or surgical intervention to prevent one of the other outcomes listed in the above definitions.

Examples of such events are intensive treatment in an emergency room or at home for allergic bronchospasm, blood dyscrasias or convulsions that do not result in hospitalisation or development of dependency or abuse.

For Japan only: the following events will be handled as “deemed serious for any other reason”. AEs which possibly lead to disability will be reported as SAEs.

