### Information required

For each AE, the investigator should provide the information requested on the appropriate eCRF pages and the BI SAE form, if applicable. The investigator should determine the causal relationship to the trial medication.

The following should also be recorded as an (S)AE in the CRF and BI SAE form (if applicable):

- Worsening of the underlying disease or of other pre-existing conditions
- Changes in vital signs, ECG, physical examination and laboratory test results, if they are judged clinically relevant by the investigator.

If such abnormalities already pre-exist prior to trial inclusion they will be considered as baseline conditions and should be collected in the eCRF only. All (S)AEs, including those persisting after individual patient's end of trial must be followed up until they have resolved, have been assessed as "chronic" or "stable", or no further information can be obtained.

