6.6 HANDLING OF MISSING DATA AND OUTLIERS

Assessment of relapse data (primary endpoint):

All patients will be followed up for relapse [...]. Any patient who has not relapsed will be censored in the analysis of the primary endpoint at the time of their planned complete 28-week treatment period. This does not include the T/W period. For AEs that meet the primary endpoint criteria, missing or incomplete AE dates are imputed according to BI standards.

The sensitivity analysis will use the Full Follow-up period to demonstrate the robustness of the results of the main analysis. See revised CTP Section 7.3

PANSS positive symptoms (key secondary analysis)

Change from baseline in PANSS positive symptoms will be evaluated using Mixed effect Model for Repeated Measures (MMRM) approach. This approach allows for missing data, assuming they are missing at random. All patients can be included in the model and missed visits will not be imputed. If a PANSS item is missing, the missing score on that individual PANSS item will not be imputed; if individual PANSS item is missing within a PANSS subscale, this subscale cannot be included in the calculation of the overall PANSS total score. Therefore, patients with missing individual PANSS items will also have a missing PANSS total score at that visit. However, subscale scores will be used for analysis if none of the individual items are missing.

Relative Risk Reduction (RRR)

Per revised CTP Section 7.5.:

All patients in the FAS will be included [...] *regardless of drop-out.*

For

AE dates

Missing or incomplete AE dates are imputed according to BI standards (see "Handling of missing and incomplete AE dates") (3).

PK data

Missing data and outliers of PK data are handled according to Reference (2) and as described in Section 10 of the revised CTP.

In December 2019, during the conduct of the trial, a Visit 8 eCRF page was added to capture
the date and time of the last dose of BI drug intake before the PK sampling performed at Visit
8. For patients who had completed the trial at that time, or patients for whom the visit 8 date
had passed, the data will be used to inform the date and time of the last BI drug
intake.
Sensitivity analysis: the date and time of the last dose of BI drug intake at Visit 8 collected in
the eCRF will be compared to the information recorded in This will be done for

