7.8.1 Adverse events

Unless otherwise specified, the analyses of adverse events will be descriptive in nature. All analyses of AEs will be based on the number of subjects with AEs and NOT on the number of AEs.

For analysis multiple AE occurrence data on the CRF will be collapsed into an AE provided that all of the following applies:

- All AE attributes are identical (LLT, intensity, action taken, therapy required, seriousness, reason for seriousness, relationship, outcome, AE of special interest)
- The occurrences were time-overlapping or time-adjacent (time-adjacency of 2 occurrences is given if the second occurrence started on the same day or on the day after the end of the first occurrence).

For further details on summarization of AE data, please refer to (3, 4).

The analysis of adverse events will be based on the concept of treatment emergent adverse events. That means that all adverse events occurring between first drug intake till last drug intake + residual effect period will be assigned to the randomised treatment. All adverse events occurring before first drug intake will be assigned to 'screening' and all adverse events occurring after the residual effect period will be assigned to 'post-treatment' (for listings only). For details on the treatment definition, see Section 6.1.

According to ICH E3 (5), AEs classified as 'other significant' need to be reported and will include those non-serious and non-significant adverse events with:

(i) 'action taken = discontinuation' or 'action taken = reduced', or

Proprietary confidential information © 2021 Boehringer Ingelheim International GmbH or one or more of its affiliated companies

(ii) marked haematological and other lab abnormalities or lead to significant concomitant therapy as identified by the Clinical Monitor/Investigator at a Medical Quality Review Meeting.

An overall summary of adverse events will be presented.

The frequency of subjects with adverse events will be summarized by treatment, primary system organ class and preferred term. Separate tables will be provided for subjects with other significant adverse events according to ICH E3 (5), for subjects with adverse events of special interest (detailed in section 5.2.6.1 of the revised CTP) and for subjects with serious adverse events.

The system organ classes will be sorted alphabetically, preferred terms will be sorted by frequency (within system organ class).

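### On-treatment relapses recorded as adverse events enter the AE and SAE totals and the psychiatric rows, and no visible passage plans a summary with and without them

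*Protocol*

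**What the plan says.** **Recording.** Under the heading on information required, Protocol 5.2.6.2 names "Worsening of the underlying disease or of other pre-existing conditions" as something that should be recorded as an (S)AE. It makes no exception for events that count as relapse. Protocol 5.2.5.1 is stricter: "All C-SSRS reports of suicidal ideation type 4 or 5 and all reports of suicidal behavior must be reported as separate SAEs by the investigator". The SAE definition in 5.2.6.1 includes inpatient hospitalisation.

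**Endpoint.** Protocol 2.1.2 defines relapse by the earliest of six criteria. The first includes hospital admission for decompensation. The fifth is suicidal behaviour or type 4/5 ideation on the C-SSRS. SAP 6.6 recognises the overlap: "For AEs that meet the primary endpoint criteria, missing or incomplete AE dates are imputed according to BI standards".

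**Tables.** Protocol 7.3.4 plans descriptive AE tables by system organ class (SOC) and preferred term (PT), with severity and causal relationship. They cover first dose to 7 days after last dose. SAP 7.8.1 adds an overall summary and separate tables for SAEs, AEs of special interest and other significant AEs. It sends events after the 7-day window to listings. On counting it says: "All analyses of AEs will be based on the number of subjects with AEs and NOT on the number of AEs". Neither section, as far as it is visible, identifies relapse-derived AEs or plans a table without them.

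**The concern.** A relapse that is recorded as an AE is counted once for efficacy and once for safety. If BI 409306 prevents relapse, the active arms will show fewer AEs and SAEs for that reason alone. A drug-related excess of other events could then be cancelled in the overall lines. Because each patient counts once per line, the non-relapse totals cannot be recovered by subtracting SOC or PT rows: a patient with a relapse SAE and another SAE is one patient in the total.

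The issue is sharpest in the psychiatric rows, where a drug-caused psychiatric event sits beside relapse. Protocol 1.4 does not exclude an effect of this centrally acting drug on suicidality.

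The previous schizophrenia trial, 1289.6, shows one contrast being used on both sides. Protocol 1.2 reports of its SAEs: "including 8/8 psychiatric SAEs, were only reported in the placebo group vs. none in the active arms". Protocol 1.3 takes this as support for efficacy, and Protocol 4.1.2 cites the absence of SAEs on active drug when choosing the doses.

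**Working it through.** **1. The plan's own figures (Protocol 7.7).** Inputs: placebo relapse 30%, hazard ratio 0.50, 258 active and 129 placebo, two-sided alpha 0.05, power 80%, dropout 20%.

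- Events (Schoenfeld): (1.960 + 0.842)² / [(1/3)(2/3)(ln 0.5)²] = 73.5, so 74, as stated.
- Sample size: with exponential relapse and dropout, the event probability is λ/(λ+δ) × (1 − e^−(λ+δ)), with δ = −ln 0.8 = 0.223. Placebo, λ = 0.357: 27.1%. Active, λ = 0.178: 14.7%. The 1:2 weighted mean is 18.8%, and 73.5 / 0.188 gives about 391, within 2% of the stated 385.

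The design assumptions are therefore a sound basis for the expected relapse load.

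**2. Relapse risk by arm, before dropout.** Placebo 30.0%, or 38.7 of 129. Active 1 − 0.7^0.5 = 16.3%, or 42.1 of 258. The gap is 13.7 points.

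**3. Model for a summary line.** Let r be the relapse risk, f the share of relapses that enter the line (recorded, inside the window and, for SAEs, serious), and b the risk of a non-relapse event, taken as independent of relapse.

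- Line total = 1 − (1 − b)(1 − f·r).
- The active-arm b that makes the two lines equal is 1 − (1 − placebo total)/(1 − f·r_active). Its excess over the placebo b is what the line can offset.

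The documents give neither f nor b, so both are assumptions.

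**4. Any SAE, with b = 4% assumed.** Take f = 0.5.

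- Without drug harm: placebo 1 − 0.96 × 0.85 = 18.4%; active 1 − 0.96 × 0.918 = 11.8%.
- Equal lines: active b = 1 − 0.816/0.918 = 11.1%. The excess is 7.1 points, about 18 of 258.

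| f (share serious) | Placebo total | Active b for equality | Offset |
|---|---|---|---|
| 0.3 | 12.6% | 8.1% | 4.1 points (about 11 patients) |
| 0.5 | 18.4% | 11.1% | 7.1 points (about 18) |
| 0.7 | 24.2% | 14.4% | 10.4 points (about 27) |

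With b = 2% and f = 0.5 the offset is 7.3 points, so the background matters less than f.

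**5. Any AE.** For scale only, 1289.6 had 33.3% (10 mg) to 53.5% (100 mg) of patients with any AE (Protocol 1.2). Offsets in points:

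| Background b | f = 0.5 | f = 1 |
|---|---|---|
| 20% | 6.0 | 13.1 |
| 33.3% | 5.0 | 10.9 |
| 50% | 3.7 | 8.2 |

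Example: with b = 33.3% and f = 1, both lines read 53.3% when the active non-relapse risk is 44.2%.

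**6. Dropout.** With relapse at 27.1% and 14.7%, the offsets shrink by about a tenth (9% to 13% across the cases run). For SAEs with f = 0.5 and b = 4%: placebo total 1 − 0.96 × (1 − 0.5 × 0.271) = 17.0%; equalising active b = 10.4%; offset 6.4 points instead of 7.1.

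**The case against.** A reader might infer that every relapse must be recorded as an AE, so that the whole primary outcome sits inside the safety comparison. The documents do not support that. The general rule in Protocol 5.2.6.2 says *should*, and no AE rule names relapse as such. Homicidal ideation and property damage become AEs only through the general definition. Self-injury without suicidal intent follows the ordinary AE/SAE rules. A relapse more than 7 days after stopping drug counts in the ITT efficacy analysis but appears only in AE listings. The window does not remove the issue, however: relapse is not a listed reason for stopping treatment (Protocol 3.3.4.1), and the patient may stay in the trial (6.2.2).

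A reader might also infer that the AE tables separate nothing. In fact the SOC, PT and causality breakdowns keep visual, cardiac and hepatic events in their own rows whatever relapse does. The safety analysis is descriptive, and nothing in the documents says that tolerability will be judged on the totals. This limits the issue to the totals and the psychiatric rows.

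Nor does 1289.6 show hidden harm. It had no SAEs on any active dose, and its psychiatric SAEs were looked at separately. That favours separating them here.

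Two further points stand. The offset sizes depend on assumed inputs and on a true hazard ratio of 0.5. And SAP 7.8.1 refers to internal AE standards that are not available here, so only the visible text can be judged.

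**Conclusion.** The point holds in a limited form. Relapses recorded as AEs within the on-treatment window enter the any-AE and any-SAE totals and the psychiatric rows. No visible passage plans those summaries with and without them. If the drug reduces relapse, these lines mix benefit with harm.

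Before dropout, the any-SAE line could offset about 4 to 10 points of excess non-relapse SAEs, assuming 30% to 70% of relapses are serious and a 4% background. The any-AE line could offset about 4 to 13 points, assuming half to all relapses are recorded and a 20% to 50% background. All of this presumes the design effect and independence of relapse and other events. With no drug effect there is no systematic offset, only added noise.

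Recruitment stopped early (SAP 4), so patient counts will be below those shown, but the mechanism is unchanged. The primary analysis, the sample size and AE collection are not affected. This is an inexpensive improvement to the safety presentation.

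**What to change.** Change SAP 7.8.1 only. Derive a flag, by relapse criterion, for AEs that meet the primary endpoint criteria; SAP 6.6 already refers to such AEs. Present three outputs twice, once with all events and once excluding flagged relapse records: the overall AE summary, the SAE table and the psychiatric SOC table. Keep suicidal behaviour and type 4/5 ideation in both versions, because Protocol 1.4 treats suicidality as a possible drug effect and excluding it would take a named safety concern out of view.

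No eCRF change and no change to AE collection or reporting is needed. The cost is one derived variable and a few repeated tables. The limits should be stated with the tables: worsening below the relapse threshold and relapses defined by suicidality remain in both versions, so the second set reduces the mixing but does not remove it.

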### **Pregnancy**

In rare cases, pregnancy might occur in a clinical trial. Once a patient has been enrolled in the clinical trial and has taken trial medication, the investigator must report any drug exposure during pregnancy in a trial participant immediately (within 24 hours) by means of Part A of the Pregnancy Monitoring Form to the sponsor's unique entry point.

The outcome of the pregnancy associated with the drug exposure during pregnancy must be followed up and reported to the sponsor's unique entry point on the Pregnancy Monitoring Form for Clinical Trials (Part B).

The ISF will contain the Pregnancy Monitoring Form for Clinical Trials (Part A and B).

As pregnancy itself is not to be reported as an AE, in the absence of an accompanying SAE and/or AESI, only the Pregnancy Monitoring Form for Clinical Trials and not the SAE form is to be completed. If there is an SAE and/or AESI associated with the pregnancy an SAE form must be completed in addition.

## **5.3 DRUG CONCENTRATION MEASUREMENTS AND PHARMACOKINETICS**

### **5.3.1 Assessment of Pharmacokinetics**

#### BI 409306:

Blood samples will be collected as indicated in the [Flow Chart](#) to measure plasma concentrations of BI 409306 and metabolites.

From the data collected after first dose, the following individual pharmacokinetic parameters will be reported:

- $C_{0.45h}$ : measured plasma concentration of BI 409306 in plasma 0:45 h after single dose of BI 409306.
- $C_{1.5h}$ : measured plasma concentration of BI 409306 in plasma 1.5 h after single dose of BI 409306.
- $C_{2h}$ : measured plasma concentration of BI 409306 in plasma 2 h or more after single dose of BI 409306.

From the individual pharmacokinetic parameters  $C_{0.45h}$  and  $C_{1.5h}$ , mean pharmacokinetic parameters will be calculated by descriptive statistics if data allow.

At the post-randomisation visits, the following pharmacokinetic parameters will be reported for each analyte:

-  $C_{\text{press}}$ : residual concentration of BI 409306 and metabolites CD 13896 and CD 14084 in plasma measured after last dose of BI 409306.

See [Section 10](#) for additional information.

